6.1 Data Handling

6.1.1 Missing Data Imputation

Unless otherwise noted, if an observation is missing at a specific scheduled visit/time point, the value at that visit will not be imputed and will be set to missing.

For the time to event endpoints, early discontinued subjects will be followed up at day 28 and day 90 to collect information on liver transplantation, subject survival, and cause of death, but the unobserved event date after last contact will not be imputed. If the date of death is not recorded in the vital status eCRF page but death is recorded as the reason for the early termination on the end of study/early termination eCRF page, then the early termination date can be used as the date of death for the time to event endpoints

For longitudinal efficacy outcomes, the mixed-effects model for repeated measurement (MMRM) and generalized linear model implemented in SAS proc GENMOD will be used to model the incomplete data. Missing data will be not explicitly imputed.

6.1.2 Day 1 Definition and Study Drug Administration

The Day1 visit is the planned date of randomization and typically, also the date of the first infusion of study treatment. In general, for baseline characteristics, disease history, medical history as well as efficacy endpoints, the Study Day 1 refers to the date of randomization (from the 'ELIGIBILITY' eCRF), while for previous and concomitant medications, exposure, and safety endpoints, the Study Day 1 refers

Instituto Grifols, S.A. / Protocol IG1407

to the date of the first exchange of study treatment or the randomization date for SMT Alone. For SMT and PE-5% if the date of randomization and the date of the first exchange of study treatment are different, the study day will not be the same for all endpoints.

All efficacy and safety assessments at all visits will be assigned a study day relative to Study Day 1.

Study day or relative day for an event/assessment visit on or after the respective Study Day 1 (\geq date of Study Day 1) is defined as:

Event date/Assessment Visit date - (Study Day 1 date) + 1

Study day or relative day for an event/assessment visit prior to the respective Study Day 1 ($<$ date of Study Day 1) is defined as:

Event date/Assessment Visit date - (Study Day 1 date)

There is no 'Day 0'.

6.1.3 Definition of Baseline

Baseline is defined as the last measurement collected on or prior to randomization date for SMT Alone, and as the last measurement obtained before the initiation of treatment (date/time) for SMT+PE-A 5%. "For SMT+PE-A 5% subjects, two sets of vital signs assessments are collected on Day 1; the time of vital signs assessment, as well as the time for lab assessment, including chemistry, coagulation and hematology parameters will be used to determine whether the vital signs or lab were collected pre- or post- Albutein administration, if assessment time is not available, then the vital signs or lab designated by the investigator as pre-dose on the Electronic Case Report Form (eCRF) will be considered baseline.

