6.1.6 Adverse Events

AEs will be classified as treatment-emergent AEs (TEAEs) or non-TEAEs based on the comparison of AE onset date/time with the start date/time of study treatment. A TEAE is defined as an AE which occurs between the start of study treatment and the final visit of the clinical study. For the SMT + PE-A 5% treatment group, start of study treatment is defined as an AE occurring during or after the first plasma exchange. For the SMT treatment group, it is assumed that subjects were already receiving SMT per institutional standards at the time of randomization; therefore, the start of study treatment will be defined as an AE occurring at or after randomization.

A non-TEAE will be defined as an AE which occurs prior to the start of study treatment.

An AE with incomplete start date/time will be determined to be a TEAE or non-TEAE using the conservative rule specified in [Appendix 3](#).

Adverse events with missing end date will be considered ongoing.

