6.4.1 Safety Population

The Safety population is defined for the SMT + PE-A 5% treatment group as the subset of subjects who received at least one PE-A 5% treatment; and is defined for the SMT alone treatment group as all subjects randomized to SMT, assuming that all subjects in the SMT arm received the SMT treatment. Safety analyses will be based on this population. Subjects will be grouped according to the treatment they actually received in all safety analyses.

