6.4.2 Intent-to-Treat (ITT) Population

The ITT population is defined as subjects who are randomized. The ITT population will be used for all efficacy analyses. Subjects will be grouped according to the treatment to which they are randomized in all efficacy analyses.

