The total CLIF-C OF score is a discrete numeric value in the range of 6 to 18 (inclusive) and is defined as the sum of the six organ/system sub-scores. If an individual sub-score is missing, the total score will also be missing. The total CLIF-C OF score and change in total score from baseline to each scheduled post-baseline visit will be summarized, as a continuous variable, by treatment and scheduled visit, excluding visits that follow liver transplantation. In addition, the total score change from baseline for scheduled visits with data for both treatment groups will be analyzed by MMRM, which includes change from baseline as the dependent variable; treatment, visit, region (Europe of North America) and ACLF subgroup (ACLF-1B, ACLF-2, or ACLF-3a), treatment-by-visit interaction, region-by-visit interaction, and ACLF subgroup (ACLF-1B, ACLF-2, or ACLF-3a)-by-visit interaction as fixed effects; baseline and baseline-by-visit as covariates; and measures within-subject at each visit as a repeated measure. The model employs an unstructured covariance matrix for the within-subject dependence. The treatment effect will be evaluated using the full model, with no backward or stepwise selection methods. If the model fails to converge, the mixed effects model with a compound symmetry correlation structure will be used.

Assessments after Liver transplant will be removed from summaries and analysis.

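### SAP 6.1.3 ties the PE-arm baseline to the first exchange while efficacy days run from randomization, so a late start gives that arm alone a post-randomization baseline, and a never-exchanged subject has no settled baseline rule

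*SAP*

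**What the plan says.** SAP 6.1.3 uses a different anchor in each arm. For control: "Baseline is defined as the last measurement collected on or prior to randomization date for SMT Alone". For the exchange arm: "as the last measurement obtained before the initiation of treatment (date/time) for SMT+PE-A 5". SAP 6.1.6, written for adverse events, shows what initiation means in that arm: "start of study treatment is defined as an AE occurring during or after the first plasma exchange".

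The efficacy clock has a single anchor. SAP 6.1.2 states that for baseline characteristics, histories, "as well as efficacy endpoints, the Study Day 1 refers to the date of randomization". It foresees that randomization and first exchange may fall on different days: if the randomization date and "the date of the first exchange of study treatment are different, the study day will not be the same for all endpoints".

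Absent exchange is also foreseen. The PE part of the Safety population is "the subset of subjects who received at least one PE-A 5% treatment" (SAP 6.4.1), whereas ITT is everyone randomized and "The ITT population will be used for all efficacy analyses" (SAP 6.4.2).

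Baseline enters the exploratory models directly. The MMRM in SAP 9.3.2 has change from baseline as its response and "baseline and baseline-by-visit as covariates". Sections 9.3.3 to 9.3.6 reuse that model. The ordinal sub-score models adjust for the baseline sub-score, and ACLF course (9.3.7) is judged against baseline. SAP 6.1.1 does not impute missing longitudinal values.

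**The concern.** Two situations that the SAP itself anticipates are handled differently by arm.

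The first is the late starter. A PE subject first exchanged a day or more after randomization takes a baseline from after randomization; a control subject never does. Treatment assignment is known by then, and Protocol 2.7 describes ACLF as changing quickly in either direction, so that value may already differ from the randomization value. The same record can also be counted as a post-baseline visit.

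The second is the subject randomized to PE-A 5% but never exchanged. This subject is in ITT, but the event that defines the baseline never happens. Such subjects are unlikely to be typical patients, and control subjects cannot be affected in this way.

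At stake is whether the exploratory change analyses are the like-for-like ITT comparison that SAP 9.3 announces, and whether two programmers working from the same SAP would derive the same change scores and the same number analyzed.

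**Working it through.** **Late starters.** Inputs: the study-day formula in SAP 6.1.2 (date minus Day 1 date, plus 1), Day 1 = randomization date R for efficacy, and the windows in SAP Appendix 5. Take a value recorded just before the first exchange, which is the 6.1.3 baseline. With a delay of d days, its efficacy study day is (R + d) − R + 1 = d + 1.

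| Delay d | Study day | Exploratory window | Laboratory window, counted from randomization |
|---|---|---|---|
| 0 | 1 | Baseline | Baseline |
| 1 | 2 | Treatment Day 2 | Treatment Day 2 (days 2 to 3) |
| 2 | 3 | Treatment Day 3 | Treatment Day 2 (days 2 to 3) |
| 3 | 4 | Treatment Day 4 | Treatment Day 4 (days 4 to 5) |

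With no delay there is no overlap. For d ≥ 1 the baseline record also lies in a post-baseline window. If it is the record selected there, its change is x − x = 0. SAP 6.1.5 chooses among several records in one window but does not exclude a record already used as baseline. On the safety clock (Day 1 = first exchange) the same value is always Day 1, so no overlap arises.

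The case is clearest for CRP, WBC and procalcitonin. They are scheduled on Days 1 and 2, and SAP 9.3.6 selects the pre-exchange value in the PE arm.

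**Size, with assumed rates.** If a share k of the PE arm starts one day late and all have the same true Day 2 change D, the observed PE mean is (1 − k)·D + k·0 = (1 − k)·D.

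- k = 5%: 0.95·D
- k = 10%: 0.90·D
- k = 20%: 0.80·D
- k = 30%: 0.70·D

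**Never-exchanged subjects.** The SAP's baseline rules, side by side:

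- 6.1.3: before the first exchange in the PE arm; no rule if there is none.
- 9.3.3 and 9.3.4: repeat the start-of-treatment anchor for the PE arm.
- 9.3.2 and 9.3.5: before treatment day 1, with no split by arm.
- Appendix 5, exploratory table: screening or Treatment Day 1 records at study day 1 or earlier map to the Baseline visit. SAP 6.1.5 says analysis visits feed all efficacy summaries.

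The first two leave such a subject without an anchor; the last two supply a baseline from screening or Day 1. No sentence ranks them. The version history shows that SAP 2.0 both updated 6.1.3 and added Appendix 5, so neither clearly replaces the other.

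For scale only, the planned arm size is 190. It is reproducible: a chi-square test of 50% against 35% at two-sided 5% and 80% power needs 170 per arm, and 170/0.9 gives 189. If 1% to 10% were never exchanged (assumed), that is 1.9 to 19 of 190. The study ended early, so 190 is not the final size and the percentages are the safer form.

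**The case against.** The anchor has a basis in the protocol. Protocol 9.1.2.4 takes baseline as the last value before study treatment starts on Day 1, and SAP 6.1.6 starts treatment at randomization for SMT and at first exchange for PE. On that view both arms are anchored on start of treatment. This explains the wording, but it does not give both arms the same relation to randomization once the two dates differ, and it does not cover a subject who never starts.

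A reader might infer that never-exchanged PE subjects certainly have no baseline and fall out of the ITT change analyses. The documents do not support that: it follows from 6.1.3 read alone, while Appendix 5, 9.3.2 and 9.3.5 would give them a baseline. Exclusion is possible, not established.

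A reader might also infer that every late starter's baseline doubles as Treatment Day 2. That too goes further than the text. In the one-day exploratory windows it takes a delay of exactly one day, a record that day before the exchange, and 6.1.3 prevailing over the Appendix 5 Baseline visit. In the laboratory windows a two-day delay can do the same; longer delays fall in later windows. The time-based pre/post rule in 6.1.3 names only vital signs and laboratory values. A severity score recorded by date alone cannot be placed before a same-day exchange, so a forced zero is not shown for those scores.

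Finally, SAP 6.1.2 says the two dates typically coincide, so late starts may be few. All of these limits stand. They narrow the point but leave the conflict between rules unresolved.

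**Conclusion.** The point holds in limited form. A stated rule gives the PE arm alone a post-randomization baseline whenever the first exchange falls after the randomization date. With a one-day delay (up to two days in the laboratory windows) and a pre-exchange record, one record can serve as both baseline and Treatment Day 2, with zero change. For never-exchanged subjects the SAP holds competing rules and does not say which governs.

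The scope is the exploratory analyses that use a baseline value. The primary endpoint and both secondary endpoints run from randomization, use no baseline measurement (SAP 9.1.1, 9.2.1, 9.2.2) and are untouched; sample size and power do not change.

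The size cannot be fixed from the documents, which give no rate of late or absent exchange. The 0.95 to 0.70 attenuation rests on assumed late-start shares of 5% to 30%, equal true change in all subjects, and 6.1.3 governing over Appendix 5. The point should be corrected, but it does not threaten the trial's main conclusions.

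**What to change.** In SAP 6.1.3, define one efficacy baseline for both arms: the last measurement on or before the randomization date and before any exchange. State that it applies to subjects randomized to PE-A 5% who are never exchanged. Align 9.3.2 to 9.3.5 and Appendix 5 with it. Add to 6.1.5 that a record used as baseline cannot also fill a post-baseline window. Keep the first-exchange reference for safety summaries and for pre/post-exchange differences.

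The cost is a few sentences and one change to the baseline flag derivation; no new data are needed. There are two downsides. The rule departs slightly from the wording of Protocol 9.1.2.4, so it should be listed in SAP section 12. Procalcitonin is not scheduled at screening, so a subject without a qualifying Day 1 sample would have no baseline for that marker; the SAP should say so, in the same terms for both arms.

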6.1.4 Definition of Last Contact Date

The last contact date is defined as the last observation recorded in the eCRF or other sources of study data (e.g., laboratory data) which provide proof of being alive. The following lists the dates to be considered for status of being alive.

- Date of visit (regular and unscheduled visits)
- Study drug plasma exchange session start date
- Liver transplant date
- AE start date
- AE end date, with Outcome not "Fatal"
- Hospital discharge date
- Disease-related complication date
- Blood product start date
- Prior/concomitant medication start/end date
- Date of subject completion or withdrawal
- Date of liver transplant/vital status assessment, with survival status not "Dead"
- Death date

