9.1 Primary Endpoint

9.1.1 Time to Death Through Day 90 After Randomization

Time to 90-day overall survival will be calculated as the earlier of [(date of death) – randomization date] for those subjects who died without having liver transplant on or prior 90 days. Subjects who did not die, or had a liver transplant before death will have their time to event censored at the earlier of the following times:

- Date of last contact.
- Liver transplant date
- Cut-off date (i.e. 90 days) for analysis

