9.2.2 Time to Death Through 28-Day After Randomization

Time to 28-day overall survival will be calculated as [date of death – randomization date] for those subjects who died without having liver transplant on or prior to 28 days. Subjects who did not die or had a liver transplant before death, will have their time to event censored at the earlier of the following times:

- Date of last contact.
- Liver transplant date
- Cut-off date (i.e. 28 days) for analysis

This endpoint will be analyzed in the same way as outlined in section 9.1.2 for the primary analysis. The probability of event-free survival for the endpoint at day 28 for the endpoint and 95% confidence interval (CI) will be estimated.

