9.3.10 Rate of New Infections

The annualized rate of new infections for a subject is defined as (number of infections for the subject) / (study duration in years for the subject). The study duration in days is defined as (end of study date - randomization date+1). The study duration in years also known as the person-year is defined as (study duration in days) / 365.25. A new infection is defined as an AE categorized as an infection or any disease related complication considered an infection i.e. spontaneous bacterial peritonitis or an infection captured as “other” and described as an infection on the disease related complications CRF page with a start date on or after the randomization date to the end of study. The annualized rate of new infection per subject will be summarized by treatment group as continuous variable.

The rate of new infections will be compared between treatment arms using a generalized linear model procedure for Poisson regression with adjustment for overdispersion using the Pearson statistic to estimate the scale parameter. The response variables in the model will be the number of new infections for each subject after randomization to the end of study. The model will include treatment group, region (Europe or North America) and ACLF grade (ACLF-1b, ACLF-2, or ACLF-3a) as collected from IWRS as fixed effects. The natural logarithm of the subjects’ study duration will be used as an offset variable in the model to adjust for subjects having different study durations. For each treatment group the mean yearly rate of new infections and corresponding two-sided 95% confidence intervals (CI) is presented. The estimated treatment effect (i.e. the incidence rate ratio of SMT + PE-A 5% versus SMT alone) and corresponding two-sided 95% CI will be presented also.

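### The last-contact rule counts the completion/withdrawal date as proof of life without requiring contact, so 90-day mortality can be understated

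*SAP*

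**What the plan says.** SAP 6.1.4 sets the standard for last contact as study data "which provide proof of being alive" and then lists dates to be considered. One is "Date of subject completion or withdrawal", with no condition attached. Two other items are conditional: an AE end date is excluded if the outcome was fatal, and a vital-status date is excluded if the subject was recorded as dead.

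SAP 9.1.1 censors subjects without an event at the earliest of last contact, liver transplant and "Cut-off date (i.e. 90 days) for analysis". SAP 9.2.2 does the same with "Cut-off date (i.e. 28 days) for analysis". SAP 9.2.1 (90-day transplant-free survival) also uses last contact.

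On missing follow-up, SAP 6.1.1 says that "early discontinued subjects will be followed up at day 28 and day 90" for survival and transplant information, "but the unobserved event date after last contact will not be imputed". None of the sensitivity analyses in SAP 9.1.3 or 9.2.3 removes the completion/withdrawal date from the last-contact list.

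SAP 9.3.10 ends person-time for the exploratory infection rate at the end-of-study date, not at last contact.

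**The concern.** Last contact is the latest of the listed dates, so one late date overrides all the others. For a subject who completes, or who withdraws at a visit or call, the completion/withdrawal date is sound evidence of life. For a subject who cannot be reached it may not be. Neither document says how the date is set in that case. Loss to follow-up is not among the withdrawal reasons in Protocol 5.3.3. Two reasons that are listed, a sponsor request and termination by a regulatory authority, do not require the subject to be seen that day.

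If the recorded date is later than the true last contact, the interval between them counts as observed and event-free. Deaths in that interval are unknown, so the number of observed deaths stays the same while time at risk grows and Kaplan-Meier mortality falls. This reaches the primary endpoint and both secondary endpoints. The treatment comparison is at risk if such losses differ by arm, which is possible in an open-label trial.

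**Working it through.** **Inputs from the plan.** SAP 6.2 gives 90-day mortality of 50% (SMT) and 35% (PE-A), exponential survival and 10% drop-out. SAP 9.1.1 and 9.2.2 give the cut-offs of 90 and 28 days.

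**Assumptions, because the documents give no figures.** These are the fraction of an arm affected, when those subjects were truly last seen, and how late their recorded date is. Loss is taken as unrelated to prognosis, and transplants are ignored.

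**The plan's own figures.** The hazards are −ln(0.50)/90 = 0.0077 and −ln(0.65)/90 = 0.00479, with ratio 0.6215 as stated. The mean event fraction is (50% + 35%)/2 = 42.5%; 141/0.425 = 332 subjects; 332/0.9 = 369, against 370 stated. The model reproduces.

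**Day 90, recorded dates all on or after Day 90.** Let a fraction f be lost evenly over Days 0-90. A death in a lost subject is seen only if it comes before the loss, with probability q = 1 − (1 − e^(−90λ))/(90λ).

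- SMT: q = 1 − 0.50/0.6931 = 0.2787
- PE-A: q = 1 − 0.35/0.4308 = 0.1875

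Everyone else is carried to Day 90, so estimated mortality is (1 − f)p + fq. At f = 10%:

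- SMT: 0.9 × 0.50 + 0.1 × 0.2787 = 0.478
- PE-A: 0.9 × 0.35 + 0.1 × 0.1875 = 0.334

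Censoring at the true last contact would give 50.0% and 35.0%. The hazard ratio (HR) is approximated by the ratio of −ln(1 − mortality) at Day 90, not by a fitted Cox model. At f = 10% it is 0.4061/0.6498 = 0.625.

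| Lost | SMT | PE-A | HR, equal loss | HR, SMT only | HR, PE-A only |
|---|---|---|---|---|---|
| 0% | 50.0% | 35.0% | 0.6215 | – | – |
| 2% | 49.6% | 34.7% | 0.6222 | 0.6295 | 0.6143 |
| 5% | 48.9% | 34.2% | 0.6233 | 0.6418 | 0.6036 |
| 10% | 47.8% | 33.4% | 0.6249 | 0.6629 | 0.5859 |

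**Shorter lags.** This case was simulated with 1,000,000 subjects per arm and 10% uniform loss. If the recorded date trails the true contact by 7, 14 or 30 days, SMT mortality reads 49.7%, 49.5% or 48.9%.

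**Day 28.** Model mortality is 19.4% (SMT) and 12.5% (PE-A). With 10% uniform loss and late dates these become 19.1% and 12.4%. If instead all 10% were last seen on Day 21, the SMT shift is 0.10 × (1 − e^(−7 × 0.0077)) = 0.10 × 5.2%, or 0.5 points.

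**Artificial bound.** If all 10% were lost at randomization, mortality would read 0.9 × 50% = 45.0% and 0.9 × 35% = 31.5% at Day 90 (HR 0.633), and SMT would read 0.9 × 19.4% = 17.5% at Day 28. Subjects are hospital inpatients at randomization, so this is a limit and not a scenario.

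**The case against.** The governing sentence in SAP 6.1.4 already demands proof of life, and the list is only of dates to consider. A date with no contact fails that standard, so a careful programmer might exclude it. That reading is available, but the list is what gets programmed, and it states no such condition. The conditions on the fatal and dead items serve another purpose: they exclude dates tied to death and do not test for contact. Their presence therefore says little about this item.

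The safeguards are real. Vital status is sought at Day 28 and Day 90 after discontinuation (SAP 6.1.1, Protocol 5.3.5), and telephone contact is allowed (Protocol Appendix 2). Day 90 procedures are requested at withdrawal. SAP 6.1.1 counts an early termination for death as a death even when the vital-status page lacks the date. These measures limit the number affected, but the rule matters exactly where they fail. Protocol 5.3.5 also limits the Day 90 procedures at withdrawal to subjects who received investigational product, while Protocol 7.2.1.3.3 and SAP 5.2.4 ask for them in all early withdrawals. Equal ascertainment across arms is therefore not assured.

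A reader might infer more than the documents support:

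- **That the date is an administrative closing date, usually after Day 90.** Neither document says so. A withdrawal date before Day 90 censors on that date and does not carry the subject to Day 90.
- **That mortality is understated as a matter of fact.** It requires failed vital-status follow-up and a late recorded date.
- **That a spurious 4.1-point difference is to be expected.** This takes 10% of one arm, all last seen alive on Day 21 and dated after Day 90: 0.10 × (1 − e^(−69 × 0.0077)) = 0.10 × 41%. Nothing in the documents supports that pattern, and the planned 10% drop-out is not an estimate of this subset.

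**Conclusion.** The point holds as a conditional one. The plan contains a rule that can set a wrong censoring time for the primary and both secondary endpoints, and no planned sensitivity analysis would reveal it. The direction is certain where a recorded date is later than true contact; the number of such subjects is unknown.

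Under 10% uniform, non-informative loss with every date on or after Day 90, the understatement is 2.2 points (SMT) and 1.6 points (PE-A) at Day 90. It shrinks to 0.3 to 1.1 points in SMT for lags of 7 to 30 days. The Day 28 effect is about 0.5 points or less outside the artificial bound. The planned comparison is nearly unaffected by equal loss and is affected materially only by one-sided loss. Losses in SMT alone pull the HR towards 1 (0.663); losses in PE-A alone exaggerate the benefit (0.586).

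Two side effects follow. The sensitivity analysis in SAP 9.1.3 for deaths without a vital-status date censors at last contact, which by this list can be the early-termination date itself. The infection rate in 9.3.10 has a parallel, minor problem in its denominator; it is exploratory and adds no weight to the survival point.

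**What to change.** In SAP 6.1.4, count the completion/withdrawal date only when it documents actual contact with the living subject, for example completion, or withdrawal at a visit or call. Otherwise use the latest other listed date that shows the subject alive. Report by arm how many censoring times rest on the withdrawal date alone. In SAP 9.3.10, end person-time at the last contact date so defined.

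The cost is one sentence in each section, a revised derivation and a short table. Protocol 5.3.3 already requires the withdrawal reason in the eCRF. The downside is slightly earlier censoring for a few subjects. If SAP version 3.0 is already being applied, the same derivation can be run as an added sensitivity analysis and documented in the clinical study report, as SAP section 2 provides.
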